Regorafenib should be taken within 2 hr after a light meal with approximately 240 mL (8 fluid ounces) of water, preferably in the morning. If necessary, the study drug may be taken at different times of the day, but there should be consistency with respect to dosing intervals (the recommendation is to have at least a 20 hr interval between doses). Tablets should not be chewed. If a dose of regorafenib is missed, the missed dose should not be made up for (vomited tablets cannot be made up), and the next dose should be taken at the regular time. The subsequent dose of regorafenib should not be doubled. The investigator should be informed if the dose of regorafenib taken exceeded the scheduled dose.

On days when pre-dose PK blood samples will be collected ([Table 8–2](#)), participants will take the morning dose of regorafenib at the clinic after all required samples are collected. On days PK samples are not required, regorafenib can be taken at home or in clinic.

Participants will continue treatment until disease progression as defined by RECIST v1.1, unacceptable toxicity or consent withdrawal, withdrawal from the study at the discretion of the investigator or his/her designated associate(s) or any other withdrawal criteria are met. Treatment beyond radiological progression is possible if the participant is still benefiting from treatment. In order to continue treatment after initial documentation of disease progression, participant must be re-consented. In case of treatment interruption or discontinuation due to Nivolumab or Regorafenib related toxicities participants may continue treatment with either Nivolumab or Regorafenib single agent respectively.

Participants who complete 24 infusions of nivolumab (after approximately 2 years of treatment) need to discontinue treatment. Regorafenib treatment can be continued until clinical disease progression, or unacceptable toxicity, or any other withdrawal criteria are met.

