Tumor assessments will be performed locally by participating radiologists/Investigators and whenever possible all scans taken at each clinical site will be interpreted by the same radiologist/Investigator at that site. Scans must meet the standard of care for imaging of lesions in the respective organ system(s). Unless progression is noted, all lesions will be assessed and reported at each scheduled scan.

All imaging scans (coded with study participant number and in digital imaging and communications in medicine [DICOM] format) as well as imaging-related adjunctive data (e.g., fluorodeoxyglucose [FDG] dose and tracer uptake time) must be prospectively collected and transferred to Bayer, or Bayer-designated imaging core lab, in case independent central review is needed.

The tumor markers CEA and CA 19-9 will be evaluated on an exploratory basis in participants with CRC and will not be used to assess objective tumor response.

Assessment of disease

RECIST v1.1 will be applied by the Investigator as the primary measure for categorization of disease on the baseline imaging and assessment of tumor response until progressive disease (see Section 10.7). CR and PR must be confirmed with repeated imaging performed at least 4 weeks after initial documentation of response.

iRECIST is based on RECIST v1.1, but adapted to account for the unique tumor response seen with immunotherapeutic drugs. iRECIST will be used by the Investigator to assess tumor response and progression, and make treatment decisions (see Section 10.8).

Tumor scans are required at screening, during study treatment and at the End of Treatment: see section 1.3 SoA Table 1–2. Tumor scans are also required during active follow-up, if applicable.

- Baseline assessments will be conducted during the screening period and target lesions should to be selected, measured, and recorded before start of study intervention. Scans that were obtained prior to the participant signing the ICF document for this study can be used as baseline assessments provided that they were performed within 28 d of starting study treatment and meet the requirements for the study

- Assessments during study treatment will be performed every 8 weeks (± 7 d) for the first year and every 12 weeks ± 14 d thereafter. Tumor assessment during the study intervention period includes the same anatomic areas as baseline and will be done until radiological disease progression or the end of the study.

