- Radiological tumor evaluation (within 14 days after last study treatment is not necessary if the previous tumor evaluation was performed within 4 weeks (for the first year) or within 8 weeks (thereafter)).
- For participants who discontinue study treatment without disease progression, FU tumor evaluations will be performed until progression of malignancy and/or start of subsequent systemic anti-cancer treatment, whichever comes first, or any other criterion for withdrawal is met. During the active FU period, CT/MRI evaluations will be performed at the same intervals as during study treatment.
- At the Investigator's discretion, tumor scans may be repeated at any time if progressive disease is suspected. For further details, see Sections 10.7 and 10.8.

For participants who show evidence of radiological PD by RECIST v1.1 and are clinically stable, the Investigator will decide whether to continue a participant on study treatment until repeat imaging is obtained using iRECIST for participant management. Participant must be re-consented for continuation of treatment beyond initial documentation of disease progression (If repeat imaging does not confirm PD per iRECIST (iCPD), as assessed by the Investigator, and the participant continues to be clinically stable, study treatment may continue and follow the regular imaging schedule. If PD is confirmed (iCPD), participants will be discontinued from study treatment).

Treatment beyond confirmed progression as per iRECIST is possible if the participant is still benefiting from treatment after documented discussion and approval by the Sponsor.

When clinically stable, participants should **not** be discontinued until progression is confirmed by the Investigator, working with local radiology, according to the rules outlined in Section 10.8. This allowance to continue treatment despite initial radiologic PD takes into account the observation that some participants can have a transient tumor flare in the first few months after the start of immunotherapy, and then experience subsequent disease response. This data will be captured in the clinical database.

For treatment beyond progression as per iRECIST the following needs to be fulfilled:

- Evidence of clinical benefit as assessed by the investigator
- Absence of symptoms and signs indicating unequivocal progression of disease.
- Absence of clinical signs or symptoms of progression despite a rising CEA level.

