- No decline in ECOG PS that can be attributed to disease progression
- Absence of tumor progression at critical anatomical sites (e.g., leptomeningeal disease) that cannot be managed by protocol-allowed medical interventions

Participant must be re-consented once for continuation of treatment beyond initial documentation of disease progression. Tumor imaging beyond progression will follow the originally planned intervals and will be conducted using iRECIST.

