The best overall response is the best response recorded from the start of the study intervention until the end of treatment. The participant's best overall response assignment will depend on the findings of both target and non-target disease and will also take into consideration the appearance of new lesions. While some non-target lesions may actually be measurable, they need not be measured and instead should be assessed only qualitatively at the time points specified in the protocol. All participants will have their Best Response on-study classified according to the RECIST v1.1 criteria as outlined below and summarized in [Table 10–3](#).

Complete Response (CR)

Disappearance of all target and non-target lesions. Any pathological lymph nodes (whether target or non-target) must have decreased in size to have a short axis of < 10 mm.

Partial Response (PR)

At least a 30% decrease in the sum of diameters of target lesions taking as reference the baseline sum diameters.

Stable Disease (SD)

Neither sufficient shrinkage to qualify for PR nor sufficient increase to qualify for PD, taking as reference the smallest sum diameters while on study.

Non-CR/Non-PD

To be used for participants with non-target lesions only at baseline. Persistence of one or more non-target lesion(s).

Progressive Disease (PD)

At least a 20% increase in the sum of diameters of target lesions, taking as reference the smallest sum on study (this includes the baseline sum if that is the smallest on study). In addition to the relative increase of 20%, the sum must also demonstrate an absolute increase of at least 5 mm. Unequivocal progression of existing non-target lesions (see comments below), or the appearance of one or more new lesions, also constitutes progressive disease.

Lymph nodes identified as target lesions should always have the actual short axis measurement recorded (measured in the same anatomical plane as the baseline examination), even if the nodes regress to below 10 mm on study. This means that when lymph nodes are included as target lesions, the 'sum' of lesions may not be zero even if complete response criteria are met, since a normal lymph node is defined as having a short axis of < 10 mm.

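### Best overall response ends at end of treatment in Protocol 10.7 but at progression in Protocol 8.1, and SAP 4.6 as written drops unscheduled tumor scans; both bear on the ORR count

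*Protocol*

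**What the plan says.** **Response window.** Protocol 9.4.2 defines a responder through best overall response. The protocol's definition of that term is in Appendix 10.7: "The best overall response is the best response recorded from the start of the study intervention until the end of treatment". A later sentence of the same paragraph speaks of best response on study, and Protocol 1.2 counts active follow-up as part of being on study. Protocol 8.1 has the investigator apply RECIST v1.1 at baseline and for "assessment of tumor response until progressive disease (see Section 10.7"), so it sends the reader to 10.7 while naming a different end point. For participants who stop treatment without progression, 8.1 adds that "FU tumor evaluations will be performed until progression of malignancy and/or start of subsequent systemic anti-cancer treatment". SAP 6.2.2 defines ORR as the percentage with CR or PR and states no window.

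**Confirmation and off-schedule scans.** Protocol 8.1 requires that "CR and PR must be confirmed with repeated imaging performed at least 4 weeks after initial documentation of response". Scheduled scans are 8 weeks apart in the first year. Protocol 8.1 also says that "tumor scans may be repeated at any time if progressive disease is suspected". SAP 4.6 keeps unscheduled visits out of the analysis and shows them only in listings. It makes no exception for tumor assessments.

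**The test.** Protocol 9.1 and SAP 6.2.2 test ORR against 5% with a one-sided exact binomial test at 2.5%. At least 8 responders among 70 are needed. Protocol 9.4.1 and SAP section 6 say that nothing else is tested.

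**The concern.** The primary endpoint is a count, and two stated rules can change who is in it.

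- **The window.** Two sections of the protocol end it at different events. Treatment can stop well before progression, for toxicity for example, and the protocol keeps scanning such participants. Whether a first response on those scans counts depends on which section the programmer follows.
- **The unscheduled-visit rule.** It is written for the whole analysis and, followed literally, reaches tumor scans. A repeat scan that meets the 4-week rule but falls between scheduled visits could be removed.

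The trial is open-label, single-arm and investigator-assessed, and a look at response data is planned before the main analysis. If these questions are left open, they may be settled when results are already known.

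**Working it through.** **1. The plan's own figures.** Inputs are n=70, null 5%, target 17% and cut-off 8 (Protocol 9.1, 9.2; SAP 6.2.1, 6.2.2). With X binomial(70, p):

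- Attained one-sided alpha: P(X≥8 | p=0.05) = 0.0234.
- With a cut-off of 7: P(X≥7 | p=0.05) = 0.0604, above 0.025. So 8 is the smallest valid cut-off.
- Power: P(X≥8 | p=0.17) = 0.9256. The stated 92.6% reproduces.

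**2. Case 1, the window.** A participant has SD at weeks 8 and 16, stops treatment at week 20 without progression, and has PR on follow-up scans at weeks 24 and 32. The two PR scans are 32 − 24 = 8 weeks apart, which satisfies the 4-week rule.

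| Rule | Window closes | Best response | Responder? |
|---|---|---|---|
| Protocol 8.1 | Progression (not yet reached) | PR | Yes |
| Protocol 10.7, end-of-treatment sentence | Week 20 | SD | No |
| Protocol 10.7, on-study sentence, with 1.2 | After active follow-up | PR | Yes |
| SAP 6.2.2 | Not stated | – | Undetermined |

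**3. Case 2, the unscheduled scan.** A participant has PR at week 16 (16 × 7 = day 112). The earliest valid confirmation is day 112 + 28 = day 140. The next scheduled scan is week 24, day 168. Suppose an off-schedule scan on day 140 shows PR and day 168 shows PD.

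- Under Protocol 8.1 this is a confirmed PR and a responder.
- Under SAP 4.6, if day 140 is recorded as an unscheduled visit, it is dropped, nothing confirms the PR, and the responder is lost.
- If day 168 still shows PR, it confirms the response (168 − 112 = 56 days) and nothing changes.

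**4. What one participant is worth.**

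| Responders | One-sided p against 5% | Clopper-Pearson 95% interval |
|---|---|---|
| 7/70 | 0.0604 | 4.12% to 19.52% |
| 8/70 | 0.0234 | 5.07% to 21.28% |

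In both cases the rule at issue removes a responder whom 8.1 would count. One such loss reverses the test when the count under 8.1 is exactly 8. Taking the true ORR as the rate under 8.1, P(X=8) is 0.0153 at 5%, 0.1374 at 10%, 0.1018 at 15% and 0.0633 at 17%. The 10% and 15% rates are assumed values between the plan's 5% and 17%. These probabilities describe how close the count is to the cut-off. They are not the chance that a participant is misclassified, for which the documents give no rate.

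**The case against.** The strongest reply is that most of this is already settled, and much of it is.

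**Responses after progression.** A reader might infer that 10.7 lets them count, because "Treatment beyond radiological progression is possible if the participant is still benefiting from treatment" (Protocol section 6) and because 8.1 notes that "some participants can have a transient tumor flare in the first few months after the start of immunotherapy, and then experience subsequent disease response". The documents do not support that. Protocol 8.1 stops RECIST v1.1 response at progression and says: "Tumor imaging beyond progression will follow the originally planned intervals and will be conducted using iRECIST". Appendix 10.8 gives later improvement its own iRECIST categories, and the primary endpoint is ORR per RECIST v1.1. The flare sentence explains why treatment may continue; it is not an ORR rule. The SAP excludes scans after first progression only under DCR, but that is a gap in cross-referencing.

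**Unconfirmed responses.** A reader might infer that they count, because Protocol 9.4.2 and SAP 6.2.2 do not mention confirmation. Section 8.1 is in force and mandatory, so an unconfirmed CR or PR does not qualify. Again only a cross-reference is missing.

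**Follow-up responses.** The on-study sentence in 10.7 supports counting them, so 10.7 is ambiguous rather than a clean exclusion. That stands, but it does not remove the conflict, since the same paragraph then points both ways.

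**Unscheduled scans.** The off-schedule allowance in 8.1 is for suspected progression, 8-weekly scans usually suffice to confirm, and the SAP's tumor-specific rule (4.3) names missing and unevaluable assessments, not unscheduled ones. This makes Case 2 conditional. It does not create an exemption that SAP 4.6 lacks.

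**Conclusion.** Two points hold. The end of the best-overall-response window differs between Protocol 10.7 and 8.1, and the SAP does not resolve it. SAP 4.6, followed literally, would also drop an off-schedule confirmatory scan recorded as unscheduled, which matters only when the next scheduled scan does not confirm.

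The consequence is limited to the boundary: a count of 8 under 8.1 becomes 7, and p moves from 0.0234 to 0.0604. How often such participants occur cannot be derived from the documents.

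A reader might infer that the rules could also inflate the count and the type-I error. That would require setting aside 8.1 on progression and confirmation; the two points that hold can only lower the count relative to 8.1. The sample size, the cut-off of 8 and the 92.6% power are correct.

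The weight is moderate: worth correcting before database lock because it touches the sole confirmatory test, but not a flaw in the design.

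**What to change.** 1. Set one window in Protocol 10.7 and SAP 6.2.2: from start of study intervention to first RECIST v1.1 progression or start of subsequent systemic anti-cancer therapy, whichever comes first, including active follow-up scans. This matches the period over which 8.1 collects scans. An on-treatment window would be a possible design choice, but it would then have to replace the wording in 8.1.
2. In SAP 4.6, exempt tumor assessments from the exclusion of unscheduled visits.
3. For clarity only, cross-reference the 8.1 confirmation rule in Protocol 9.4.2 and SAP 6.2.2, stating that an unconfirmed CR or PR is not a responder, and extend the SAP's DCR statement on scans after first progression to ORR.

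The cost is wording in two documents and no new data. The observed ORR may move slightly: up if a follow-up response or an off-schedule confirmation now counts, down if an unconfirmed response would otherwise have been counted. The sample size, cut-off and stated power do not change.

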10.8 Appendix 8: Response Assessment for CRC - iRECIST

iRECIST is RECIST v1.1 adapted as described below to account for the unique tumor response seen with immunotherapeutic drugs (Table 10–4). iRECIST will be used by site Investigator/local radiology review to make treatment decisions. This data will be collected in the clinical database

Description of the iRECIST Process for Assessment of Disease Progression

Assessment at Screening and Prior to RECIST v1.1 Progression

Until radiographic disease progression based on RECIST v1.1, there is no distinct iRECIST assessment.

Assessment and Decision at RECIST v1.1 Progression

For participants who show evidence of radiological PD by RECIST v1.1, the Investigator will decide whether to continue a participant on study treatment until repeat imaging is obtained using iRECIST for participant management (see Table 10–4 and Figure 10–1). This decision by the Investigator should be based on the participant's overall clinical condition.

Clinical stability is defined as the following:

Absence of symptoms and signs indicating clinically significant progression of disease

No decline in ECOG PS

No requirements for intensified management, including increased analgesia, radiation, or other palliative care

Any participant deemed **clinically unstable** should be discontinued from study treatment at site-assessed first radiologic evidence of PD and is not required to have repeat tumor imaging for confirmation of PD by iRECIST.

If the Investigator decides to continue treatment, the participant may continue to receive study treatment and the tumor assessment should be repeated 4 to 8 weeks later to confirm PD by iRECIST, per Investigator assessment.

Tumor flare may manifest as any factor causing radiographic progression per RECIST v1.1, including:

Increase in the sum of diameters of target lesion(s) identified at baseline to $\geq 20\%$ and ≥ 5 mm from nadir

Note: the iRECIST publication uses the terminology “sum of measurements”, but “sum of diameters” will be used in this protocol, consistent with the original RECIST v1.1 terminology.

Unequivocal progression of non-target lesion(s) identified at baseline

Development of new lesion(s)

iRECIST defines new response categories, including unconfirmed progressive disease by iRECIST (iUPD) and iCPD. For purposes of iRECIST assessment, the first visit showing progression according to RECIST v1.1 will be assigned a visit (overall) response of iUPD, regardless of which factors caused the progression.

At this visit, target and non-target lesions identified at baseline by RECIST v1.1 will be assessed as usual.

New lesions will be classified as measurable or non-measurable, using the same size thresholds and rules as for baseline lesion assessment in RECIST v1.1. From measurable new lesions, up to 5 lesions total (up to 2 per organ), may be selected as New Lesions – Target. The sum of diameters of these lesions will be calculated and kept distinct from the sum of diameters for target lesions at baseline. All other new lesions will be followed qualitatively as New Lesions – Non-target.

Assessment at the Confirmatory Imaging

On the confirmatory imaging, the participant will be classified as progression confirmed (with an overall response of iCPD), or as showing persistent unconfirmed progression (with an overall response of iUPD), or as showing disease stability or response (iSD/iPR/iCR).

Confirmation of Progression

Progression is considered confirmed, and the overall response will be iCPD, if ANY of the following occurs:

Any of the factors that were the basis for the initial iUPD show worsening

For target lesions, worsening is a further increase in the sum of diameters of ≥ 5 mm, compared to any prior iUPD time point

For non-target lesions, worsening is any significant growth in lesions overall, compared to a prior iUPD time point; this does not have to meet the “unequivocal” standard of RECIST v1.1

For new lesions, worsening is any of these:

An increase in the new lesion sum of diameters by ≥ 5 mm from a prior iUPD time point

Visible growth of new non-target lesions

The appearance of additional new lesions

Any new factor appears that would have triggered PD by RECIST v1.1

Persistent iUPD

Progression is considered not confirmed, and the overall response remains iUPD, if:

None of the progression-confirming factors identified above occurs AND

The target lesion sum of diameters (initial target lesions) remains above the initial PD threshold (by RECIST v1.1)

Additional imaging for confirmation should be scheduled 4 to 8 weeks from the imaging on which iUPD is seen. This may correspond to the next visit in the original visit schedule. The assessment of the subsequent confirmation imaging proceeds in an identical manner, with possible outcomes of iCPD, iUPD, and iSD/iPR/iCR.

Resolution of iUPD

Progression is considered not confirmed, and the overall response becomes iSD/iPR/iCR, if:

None of the progression-confirming factors identified above occurs, AND

The target lesion sum of diameters (initial target lesions) is not above the initial PD threshold.

The response is classified as iSD or iPR (depending on the sum of diameters of the target lesions), or iCR if all lesions resolve.

In this case, the initial iUPD is considered to be pseudo-progression, and the level of suspicion for progression is “reset”. This means that the next visit that shows radiographic progression, whenever it occurs, is again classified as iUPD by iRECIST, and the confirmation process is repeated before a response of iCPD can be assigned.

Management Following the Confirmatory Imaging

If repeat imaging does not confirm PD per iRECIST, as assessed by the Investigator, and the participant continues to be clinically stable, study treatment may continue and follow the regular imaging schedule. If PD is confirmed, participants will be discontinued from study treatment.

NOTE: If a participant has iCPD as defined above, but the participant is achieving a clinically meaningful benefit, an exception to continue study treatment may be considered following consultation with the Sponsor. In this case, if study treatment is continued, tumor imaging should continue to be performed following the intervals as outlined in this protocol (See [SoA Table 1–2](#))

Detection of Progression at Visits after Pseudo-progression Resolves

After resolution of pseudo-progression (i.e., achievement of iSD/iPR/iCR), iUPD is indicated by any of the following events:

Target lesions

Sum of diameters reaches the PD threshold ($\geq 20\%$ and ≥ 5 mm increase from nadir) either for the first time, or after resolution of previous pseudo-progression. The nadir is always the smallest sum of diameters seen during the entire trial, either before or after an instance of pseudo-progression.

Non-target lesions

If non-target lesions have never shown unequivocal progression, their doing so for the first time results in iUPD.

If non-target lesions have shown previous unequivocal progression, and this progression has not resolved, iUPD results from any significant further growth of non-target lesions, taken as a whole.

New lesions

New lesions appear for the first time

Additional new lesions appear

Previously identified new target lesions show an increase of ≥ 5 mm in the new lesion sum of diameters, from the nadir value of that sum

Previously identified non-target lesions show any significant growth

If any of the events above occur, the overall response for that visit is iUPD, and the iUPD evaluation process (see Assessment at the Confirmatory Imaging above) is repeated. Progression must be confirmed before iCPD can occur.

The decision process is identical to the iUPD confirmation process for the initial PD, with one exception: if new lesions occurred at a prior instance of iUPD, and at the confirmatory imaging the burden of new lesions has increased from its smallest value (for new target lesions, the sum of diameters is ≥ 5 mm increased from its nadir), then iUPD cannot resolve to iSD or iPR. It will remain iUPD until either a decrease in the new lesion burden allows resolution to iSD or iPR, or until a confirmatory factor causes iCPD.

[figure not shown]
Additional details about iRECIST are provided in the iRECIST publication (60).

Table 10–4: Imaging and Treatment after First Radiologic Evidence of PD

	Clinically Stable		Clinically Unstable	
	Imaging	Treatment	Imaging	Treatment
1 st radiologic evidence of PD by RECIST v1.1	Repeat imaging at 4 to 8 weeks at site to confirm PD	May continue study treatment at the local site Investigator's discretion while awaiting confirmatory tumor imaging by site by iRECIST.	Repeat imaging at 4 to 8 weeks to confirm PD per physician discretion only	Discontinue treatment
Repeat tumor imaging confirms PD (iCPD) by iRECIST at the local site	No additional imaging required	Discontinue treatment (exception is possible upon consultation with Sponsor)	No additional imaging required	N/A
Repeat tumor imaging shows iUPD by iRECIST per Investigator assessment	Repeat imaging at 4 to 8 weeks to confirm PD. May occur at next regularly scheduled imaging visit.	Continue study treatment at the Investigator's discretion.	Repeat imaging at 4 to 8 weeks to confirm PD per Investigator's discretion only.	Discontinue treatment
Repeat tumor imaging shows iSD, iPR, or iCR by iRECIST per Investigator assessment.	Continue regularly scheduled imaging assessments	Continue study treatment at the local site Investigator's discretion	Continue regularly scheduled imaging assessments	May restart study treatment if condition has improved and/or clinically stable per Investigator's discretion. Next tumor image should occur according to the every 6 weeks (± 7 d) imaging schedule for the 32 weeks (until Week 31 D1 ± 7 d) and 12 weeks (± 14 d) thereafter

Abbreviations: D/d = day(s); iCPD = iRECIST confirmed progressive disease; iCR = iRECIST complete response; iRECIST = modified Response Evaluation Criteria in Solid Tumors v1.1 for immune-based therapeutics; iPR = iRECIST partial response; iSD = iRECIST stable disease; iUPD = iRECIST unconfirmed progressive disease; N/A = not applicable; PD = progressive disease; RECIST v1.1 = Response Evaluation Criteria in Solid Tumors v1.1

Figure 10–1: iRECIST: Process for Assessment of Disease Progression

Abbreviation: iRECIST = immune RECIST; PD = progressive disease

